Topic: Exploring the use of Virtual Reality applications in patients with a diagnosis of motor neurone disease

BACKGROUND:

The potential benefit from using technology to improve health has been an area of growing interest within healthcare workers and researchers. This study aims to explore the use of virtual reality technology in improving health and wellbeing in people with a diagnosis of motor neurone disease (MND).

MND is a chronic progressive neurological condition which affects 1-5 people per 100,000 of population. It affects people generally in adulthood and more specifically within the 50-70 years of age. Motor Neurone disease is no longer considered to be a condition that affects the motor system alone. Extra motor clinical pathology, routinely observed in histopathological examinations, has been found with a preference for prefrontal, frontal and temporal cortices (Baumer et al, 2014). This is consequently associated with dysexecutive syndrome, behavioural impairment and, in up to 15% of cases, with overt frontotemporal dementia (Abrahams et al, 2014).

Due to the progressive nature of the condition, an individual with MND has to continue to adapt to the losses brought about by the condition. A study by Soofi et al., (2018) describes how people with MND perceive having a choice of rehabilitation interventions as important for them to have a sense of control over their life. It is believed that psychological, spiritual and social wellbeing is important for people with MND rather than a focus on physical functioning alone. Studies examining the role of psychological interventions in MND have found benefits from interventions such as meditation for promoting wellbeing in patients and their carers. Foley., (2007) highlighted the need for palliative care interventions to improve wellbeing in people with MND. Additionally, a study by Marconi et al., (2016), found that meditation helped promote a better acceptance of the condition. Furthermore, Pagnini et al., (2017) found that meditation training improved quality of life in people with MND.

More recently, the use of virtual reality (VR) technology is being recognised in the field of health management. Virtual reality refers to a technology that uses interactions between an individual and a computer generated environment which stimulates different sensory modalities such as visual and auditory (Dascal et al., 2017). This is accessed most commonly via the use of head mounted- goggles or headsets. Most of the studies published till date, have targeted the areas of pain management, eating disorders and cognitive or motor rehabilitation (Dascal et al, 2017). Schmitt et al., (2011) and Patterson et al., (2010) have suggested that the entertaining or stimulating effect of VR is useful in redirecting the

patient's attention away from distressing experiences such as those of anxiety and pain. The potential benefit of VR technology to enhance recovery after central nervous system injury continues to be an area of growing interest and one that has room for further exploration.

The use of VR has not been explored in motor neurone disease, a terminal condition, where individuals experience severe distressing symptoms from anxiety, respiratory distress or positional discomfort. Additionally, there remains limited evidence for its use in other long term conditions such as Multiple System Atrophy, Parkinson's disease or Multiple Sclerosis. Although there have been studies that look at interventions that support quality of life in motor neurone disease (Soofi et al., 2018; Pagnini et al., 2017; Marconi et al, 2016), these have not involved the use of VR technology. This study will try to explore the use of VR in this client group with a view to documenting what clients find useful, whether it affects their care needs, whether it helps with enhancing wellbeing and reducing anxiety.

Care of individuals with a diagnosis of motor neurone disease, is based on supportive interventions that help to improve quality of life. This study examines the role of VR and its impact on the quality of life in this client group. It is hoped that if this intervention is found beneficial in this client group then it may pave the way for its use in other similar long term conditions where supportive interventions are beneficial.

METHOD:

30 patients with a diagnosis of MND, who consent to taking part, will be included in the study based on a set of Inclusion/Exclusion criteria.

Inclusion Criteria:

- 1) Diagnosis of MND
- 2) Sufficient cognitive ability to understand instructions with regards using the VR kit
- 3) Has sufficient motor ability/dexterity to use the kit or a carer who will be able to assist with the use of the kit.
- 4) Can tolerate light and have sufficient head control to wear the head set.
- 5) Can understand English

Exclusion Criteria:

- 1) Poor cognition – inability to understand instructions regarding the use of VR.
- 2) Unable to tolerate light/unable to wear the head set
- 3) Light sensitive epilepsy, severe vertigo or dizziness.
- 4) Does not understand English

Patients will be referred to the study by members of the MND Care team. Patients meeting the Inclusion criteria and those who consent to participating will be recruited into the study.

Each of these patients will be assessed on a set of tests before and after the intervention period of 4 weeks. At the end of the intervention period, there will be a short interview to document the usage and perceived benefits (or not) of the device.

1. A test of cognition- ECAS
2. PHQ-9 for depression
3. GAD-7 for Anxiety
4. Edinburgh Mental Wellbeing scale

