5. ALS-FRS
6. A daily diary for the client/carer to document the time for which the VR device was used.

The intervention period will be for 4 weeks where patients will be required to use the VR set for 2 hours in the day. During the implementation phase, support will be provided with regards any distressing symptoms or intolerance to the sensory stimulation some patients may potentially develop, due to the introduction of this technology. If the individual continues to be unhappy, the VR set use will be discontinued and the patient will be excluded from the study. Those patients who successfully complete the 4 week intervention will be reassessed on the questionnaires and will have an interview to document the impact of VR use on them and their quality of life.

RESULTS:

The data from the study will be analysed using a combination of qualitative analysis and statistical testing. The outcome of the research will be disseminated to patients and their carers and to the wider public using other methods of dissemination such as research journal publication and research reports.

REFERENCES:

Foley, G. (2007) 'What are the care needs for people with Motor Neurone Disease and how can occupational therapists respond to meeting these needs' *British Journal of Occupational Therapy*; 70(1): 32-34.

Pagnini, F., Marconi, A., Tagliaferni, G.M., Manzoni, R., Gatto, V., Fabiani, V., Gregnano, G., Rossi, G., Volpato, E., Banfi, P., Palmieri, A., Graziano, F., Castelnuova, G., Corbo, M.,

Molinari., E., Rival., N., Sansona., V., Lunetta., C., (2017) " Meditation training for people with amyotrophic lateral sclerosis: a randomised clinical trial" *European Journal of Neurology*, 24: 578-586.

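### METHOD promises before-and-after tests for every recruited patient, then reassesses and interviews only those who complete four weeks of VR

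*Protocol*

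**What the plan says.** The aim, in BACKGROUND, is exploratory: "This study will try to explore the use of VR in this client group with a view to documenting what clients find useful". The same sentence goes on to ask "whether it helps with enhancing wellbeing and reducing anxiety".

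METHOD describes follow-up twice.

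- Directly after the recruitment paragraph: "Each of these patients will be assessed on a set of tests before and after the intervention period of 4 weeks". The end of the period also brings "a short interview to document the usage and perceived benefits (or not) of the device". Neither sentence is limited to patients still using VR.
- After the list of tests: "support will be provided with regards any distressing symptoms or intolerance to the sensory stimulation". If a patient is still dissatisfied after that, "the VR set use will be discontinued and the patient will be excluded from the study". Then: "Those patients who successfully complete the 4 week intervention will be reassessed on the questionnaires", and the same patients "will have an interview to document the impact of VR use on them and their quality of life".

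Thirty patients are to be included and all use VR. RESULTS says only that qualitative analysis and statistical testing will be combined. It does not say which measure receives which.

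**The concern.** The two accounts of follow-up do not agree on who provides 4-week data. If the second is followed, the missing patients are not a random subset, because they include those who remained dissatisfied with VR despite support. They have a known reason to report no benefit, and the interview is explicitly meant to record lack of benefit as well as benefit.

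For an exploratory study, who cannot use the device and why is a central finding. A statistical analysis plan can define analysis sets, but it cannot recover questionnaires and interviews that were never collected. The matter therefore has to be settled in the protocol.

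**Working it through.** **Step 1: the two statements side by side.**

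| | METHOD, after recruitment | METHOD, after the list of tests |
|---|---|---|
| Tested at 4 weeks | each recruited patient | those who complete |
| Interviewed | no restriction stated | those who complete |
| Patient who stops because dissatisfied | not mentioned | removed from the study |

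The second account does not literally forbid reassessing someone who stopped. Removal from the study together with the completer wording leaves no practical route to it.

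**Step 2: what remains for a patient who stops.** Baseline tests and any diary entries made before stopping remain. There are no 4-week scores and no interview.

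**Step 3: how much this could matter.** The protocol gives no figure to reproduce: it states no number expected to stop, no SD and no named test. Everything below except the 30 patients is assumed.

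*Interview.* Suppose k = 6 of 30 stop and 18 of 24 completers report benefit (18/24 = 75%). The share among all 30 is (18 + x)/30, where x is the number of the six who would have reported benefit.
- x = 0: 18/30 = 60%.
- x = 6: 24/30 = 80%.
- Same rate as completers: 75%.

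*Scores.* Let m be how much worse, in SD of change, the stoppers' mean change is than the completers'. The mean of all 30 equals the completer mean minus (k/30) × m. The completer mean therefore exceeds it by (k/30) × m.

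| k stopping | m | Completer mean minus mean of all 30 (SD) |
|---|---|---|
| any | 0 | 0 |
| 3 | 0.5 | 3/30 × 0.5 = 0.05 |
| 6 | 0.5 | 6/30 × 0.5 = 0.10 |
| 6 | 1.0 | 6/30 × 1.0 = 0.20 |
| 9 | 1.0 | 9/30 × 1.0 = 0.30 |
| 3 | -0.5 | 3/30 × (-0.5) = -0.05 |
| 9 | -0.5 | 9/30 × (-0.5) = -0.15 |

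For comparison, the 95% CI half-width of the completer mean is t(0.975, n-1)/√n. This gives 0.396, 0.422 and 0.455 SD for 27, 24 and 21 completers. Every shift in the table is smaller than that.

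*False signal.* In 60,000 simulated trials the true mean change was zero, the 6 of 30 patients with the lowest tolerance stopped, and completers' changes were tested with a two-sided 5% paired t-test. The chance of a significant result favouring VR was:
- 2.4% when tolerance and favourable change are uncorrelated (nominal 2.5%);
- about 5%, 7% and 14% at correlations of 0.2, 0.3 and 0.5;
- about 1% at -0.3.

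**The case against.** The strongest reply is that METHOD is drafted in the usual way, with a general sentence first and the detailed flow later. The later paragraph is operationally clear, so staff would know whom to reassess. That is a fair reading, and it reduces the conflict to loose wording. It also confirms that only completers provide 4-week data, which is the substance of the concern.

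Second, the loss is partial. Diaries and baseline tests exist for patients who stop, and a completer can also report no benefit. This stands: the evidence on lack of benefit is weakened, not emptied.

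Third, a reader might infer that the single-group design is itself an error, or that the protocol will present the before-after change as caused by VR. The document does not support either. The study is framed as exploration, for which one group is acceptable. It states no hypothesis, makes no causal claim, and names no test for the anxiety or wellbeing scores. BACKGROUND expresses a hope that a beneficial finding might lead to wider use, but only as a hope. What survives is a note on interpretation. With one group, change over 4 weeks cannot be separated from the course of a progressive disease, from expectation, or from the support given during the period.

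**Conclusion.** The concern holds as a point about data collection, and its severity is minor to moderate. METHOD describes two different groups to be reassessed. Under the more detailed description, the study learns nothing at 4 weeks from patients who could not get on with VR. Its findings on usefulness, wellbeing and anxiety would describe completers, and may look better than findings for all who started.

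It would be tempting to say that completer-only follow-up biases the study towards benefit. The document does not establish that. The difference is zero if stopping is unrelated to score change, and it reverses if those who stop fare better. The illustrative figures rest wholly on assumed numbers stopping, differences and correlations, so they do not set the severity. The inconsistency and the missing data need none of them.

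**What to change.** Reconcile the two METHOD paragraphs on who provides 4-week data. Leave the rule for discontinuing VR as it stands. Replace the second half of "the VR set use will be discontinued and the patient will be excluded from the study" (removal from the study) and the completer-only sentence beginning "Those patients who successfully complete the 4 week intervention will be reassessed on the questionnaires" with:

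*All patients who start VR will be offered the 4-week questionnaires and interview, whether or not they are still using VR; participation after stopping is voluntary.*

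Both existing sentences have to change. Adding the new one beside them would create a fresh contradiction.

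Report the numbers who started, stopped (with reasons) and were reassessed. Where patients who stopped are not reassessed, say that the results describe completers. Cover the assessment after stopping in the consent.

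As a note on interpretation only, report the before-after change in wellbeing and anxiety descriptively with 95% CIs, and not as an effect of VR.

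The cost is a few sentences of protocol and consent text, plus one voluntary questionnaire set and interview for each patient who stops. That is 3 to 9 patients if 10% to 30% of 30 stop, which is an assumption. The burden on patients who have already stopped is the main drawback, and is why the assessment must be optional.

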5. ALS-FRS
6. A daily diary for the client/carer to document the time for which the VR device was used.

The intervention period will be for 4 weeks where patients will be required to use the VR set for 2 hours in the day. During the implementation phase, support will be provided with regards any distressing symptoms or intolerance to the sensory stimulation some patients may potentially develop, due to the introduction of this technology. If the individual continues to be unhappy, the VR set use will be discontinued and the patient will be excluded from the study. Those patients who successfully complete the 4 week intervention will be reassessed on the questionnaires and will have an interview to document the impact of VR use on them and their quality of life.

RESULTS:

The data from the study will be analysed using a combination of qualitative analysis and statistical testing. The outcome of the research will be disseminated to patients and their carers and to the wider public using other methods of dissemination such as research journal publication and research reports.

REFERENCES:

Foley, G. (2007) 'What are the care needs for people with Motor Neurone Disease and how can occupational therapists respond to meeting these needs' *British Journal of Occupational Therapy*; 70(1): 32-34.

Pagnini, F., Marconi, A., Tagliaferni, G.M., Manzoni, R., Gatto, V., Fabiani, V., Gregnano, G., Rossi, G., Volpato, E., Banfi, P., Palmieri, A., Graziano, F., Castelnuova, G., Corbo, M.,

Molinari., E., Rival., N., Sansona., V., Lunetta., C., (2017) " Meditation training for people with amyotrophic lateral sclerosis: a randomised clinical trial" *European Journal of Neurology*, 24: 578-586.

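### Use of the VR set is recorded only by self- or proxy-report against a known 2-hour daily requirement, so misreporting in either direction cannot be detected

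*Protocol*

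**What the plan says.** The relevant statements are all in the protocol's METHOD section.

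- **Requirement.** The paragraph on the intervention period says "The intervention period will be for 4 weeks" and that "patients will be required to use the VR set for 2 hours in the day".
- **First measure of use.** Item 6 in the list of tests is "A daily diary for the client/carer to document the time for which the VR device was used".
- **Second measure of use.** The paragraph before that list says that, when the period ends, "there will be a short interview to document the usage and perceived benefits (or not) of the device".
- **Who may be reporting.** Inclusion criterion 3 reads "Has sufficient motor ability/dexterity to use the kit or a carer who will be able to assist with the use of the kit". Some patients will therefore depend on a carer to operate the kit, and item 6 allows the carer to keep the diary.
- **Who is reassessed.** "Those patients who successfully complete the 4 week intervention will be reassessed on the questionnaires". Completion is not defined in hours, and no rule connects diary entries to completion, reassessment or analysis.

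The protocol mentions no headset log or other objective record of time on the device.

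**The concern.** Use plays two parts in this study. It is an instruction with a number attached, and it is something the study sets out to document. Both planned sources are reports by the patient or carer, and both parties know the number. If a diary shows entries close to 2 hours, nothing else collected can tell the reader whether they reflect the time actually spent or the time requested. If entries are missing, nothing can tell the reader whether the set was unused or the diary was not filled in.

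Two things are at stake. The first is the account of how much people with MND used the device, which is among the more useful things a single-group exploratory study of 30 patients can report. The second is any statement of how much exposure lay behind a change in anxiety, depression or wellbeing scores. This is a choice about data collection. Use that is not captured objectively during the 4 weeks may be impossible to recover later, so the statistical analysis plan, which is not shown, could not repair it.

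**Working it through.** **Sources of information on use, side by side**

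| Source | Reporter | Knows the 2-hour figure? | Independent of report? |
|---|---|---|---|
| Daily diary (METHOD, tests, item 6) | Patient or carer | Yes | No |
| End interview (METHOD, paragraph before the tests) | Patient; the protocol does not say whether a carer contributes | Yes | No |
| Headset log or other device record | Not mentioned | – | – |

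The interview is a second source, but it has the same weakness as the diary. Agreement between the two would not confirm either.

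**Prescribed exposure**

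Inputs from METHOD: 2 hours a day; 4 weeks = 28 days; 30 patients.

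- Per patient: 2 h x 28 = 56 h.
- All patients, if everyone completes: 56 h x 30 = 1,680 h.

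The protocol gives no total of its own to reproduce.

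**How far true use could lie below a full diary**

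The documents give no figure for reporting error, so the rates below are assumptions. Over-reporting is expressed relative to true use:

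true use = reported use / (1 + over-reporting)

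| Assumed over-reporting | Calculation | True use |
|---|---|---|
| 0% | 56 / 1.00 | 56 h |
| 10% | 56 / 1.10 | 50.9 h |
| 25% | 56 / 1.25 | 44.8 h |
| 50% | 56 / 1.50 | 37.3 h |

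In daily terms the last row is 37.3 / 28 = 1.3 h instead of 2 h.

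**The other direction**

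A day on which the set was used for 2 hours but nothing was written removes 2 h from the recorded total, or 2 / 56 = 3.6% of the prescribed exposure. The protocol does not say how blank days are read, so under-recording is as open as over-recording.

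**What is not affected**

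The ECAS, PHQ-9, GAD-7, wellbeing scale and ALS-FRS are taken before and after the period. None of these scores is calculated from diary hours, and no stated rule makes diary hours a condition of being reassessed. Error in the diary therefore leaves the score changes as they are; it affects only the exposure attached to them.

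**The case against.** The strongest reply is that a daily diary is an ordinary, low-burden measure for a small exploratory study at home, and that preferring a device log is a refinement rather than the correction of an error. The diary asks for time used, not whether a target was met. The aims set out in BACKGROUND concern what patients find useful, care needs, wellbeing and anxiety; no adherence endpoint, feasibility threshold or dose-response analysis is stated. The device is not named, so it may keep no log.

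Much of this stands. It limits the weight of the point and rules out several stronger readings that a reader might infer:

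- *That the diary is the sole check on use.* It is not; the interview also documents usage. What holds is that both are reports.
- *That reported time is pulled towards 2 hours, so use cannot be measured without bias.* This is plausible but not shown. The documents give no evidence of anchoring, its size or its direction.
- *That completion is judged against the 2-hour figure, giving patients a reason to inflate entries.* No minimum use is stated. The stated ground for taking a patient out is continued unhappiness with the set.
- *That carers will fill in entries late or from the target.* Criterion 3 concerns help with operating the kit. It makes proxy entries likely for some patients but says nothing about their quality.

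The objection does not remove the core. The protocol says that usage is to be documented, and it plans nothing against which the reports can be checked.

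**Conclusion.** The point holds as a limitation of measurement. All planned information on use is self- or proxy-report against a known requirement, and misreporting in either direction would go unseen. The description of use, and of the exposure behind any observed change, may therefore be wrong.

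The size of the error is unknown. The range of 56 to 37 h of true use behind a reported 56 h rests entirely on assumed over-reporting of 0% to 50%; it illustrates the uncertainty and does not estimate it. Under-recording through missed entries is equally possible. The documents do not support a claim that bias is certain, or that the before-after questionnaire comparison is biased through this route.

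The change is worth making because it is cheap and because the data may not be recoverable later. It is an improvement to the plan and does not bear on whether the study can go ahead.

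**What to change.** In METHOD, at item 6 of the tests:

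1. Where the headset keeps a usage log, download it when the kit is returned and make it the primary measure of daily use.
2. Keep the diary as back-up and compare it with the log.
3. Ask patients and carers to record the actual time even when it is below 2 hours.
4. If the headset keeps no log, keep the diary and state that use is self-reported.

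The cost is a few protocol sentences and one download per patient at kit return, with no extra visit. The main step depends on the headset having a log, and time switched on may slightly overstate time worn.

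The protocol should not, as part of this change, tell patients how low use bears on their place in the study. That would require the sponsor first to clarify what completing the 4 weeks successfully means.

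### Stopping VR also ends study participation, so end-of-study scores, interviews and reasons are not collected from patients who stop

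*Protocol*

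**What the plan says.** The METHOD section sets the size of the study: "30 patients with a diagnosis of MND, who consent to taking part, will be included in the study". It describes a single group and no control. The general schedule covers everyone recruited: "Each of these patients will be assessed on a set of tests before and after the intervention period of 4 weeks". At the end, "there will be a short interview to document the usage and perceived benefits (or not) of the device".

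After the list of assessments, the text on the intervention period foresees "any distressing symptoms or intolerance to the sensory stimulation some patients may potentially develop" and provides support for it. It then states: "If the individual continues to be unhappy, the VR set use will be discontinued and the patient will be excluded from the study". The next sentence reads: "Those patients who successfully complete the 4 week intervention will be reassessed on the questionnaires and will have an interview".

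The aims, near the end of BACKGROUND, include "documenting what clients find useful, whether it affects their care needs, whether it helps with enhancing wellbeing and reducing anxiety".

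**The concern.** Whether a patient keeps using the headset and whether that patient stays under observation are separate decisions. The Protocol makes the second follow automatically from the first. The people removed are selected on their reaction to the intervention: they are those who remain unhappy after support.

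Two things are at stake.

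- **The accounts.** In a first exploration of VR in this disease, people who could not accept it can say for whom it fails and why. Their interviews are not sought, and nothing provides for recording their reasons.
- **The scores.** The before-after change would come from completers only. If patients who cannot tolerate VR also fare worse on mood or wellbeing, that change looks too good.

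The general schedule and the later completers-only sentence also do not agree on who is reassessed.

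**Working it through.** **1. What is collected, and from whom**

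| Item | Completers | Patients who stop |
|---|---|---|
| Baseline tests | yes | yes |
| Diary of time used | yes | up to stopping |
| 4-week tests | yes | yes under the general schedule; no under the later text |
| Interview | yes | no under the later text |
| Individual reason for stopping | not applicable | no provision |

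The later text is the more specific and would govern in practice. The number who did not complete can still be found as enrolled minus completers.

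**2. Possible size of the bias**

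The Protocol gives N = 30 but no stopping rate, SD, effect size or significance level, so there is no figure of its own to reproduce. All other inputs are assumptions: true mean change 0 across all patients; 3, 6 or 9 of 30 stop, being those lowest on a latent tolerance score; that score correlates r with change; paired t test on completers, two-sided 5%, so 2.5% in the favourable direction.

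With q the fraction removed, the large-sample bias in SD of change is r × φ(z_q)/(1 − q). For q = 0.2 and r = 0.5: 0.5 × 0.280/0.8 = 0.175. Simulating 60,000 trials of 30 patients per cell gives the bias in SD and, in brackets, the rate of falsely favourable results:

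| Stop (left) | r = 0.1 | r = 0.3 | r = 0.5 | r = 0.7 |
|---|---|---|---|---|
| 3 (27) | 0.02 (3.0%) | 0.06 (4.7%) | 0.09 (7.3%) | 0.13 (11.3%) |
| 6 (24) | 0.03 (3.6%) | 0.10 (7.2%) | 0.17 (13.7%) | 0.24 (24.9%) |
| 9 (21) | 0.05 (4.0%) | 0.15 (9.8%) | 0.24 (20.6%) | 0.34 (40.1%) |

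At r = 0 there is no bias and the rate is 2.4% to 2.7%. Analysing all 30 gives 2.4% to 2.6% in every cell.

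**3. Cross-check by another model**

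If a share d stops and completers change by D SD more favourably than stoppers, the completers' mean is too high by d × D. For d = 0.2 and D = 1.0 this is 0.20 SD. The noncentral t distribution with n = 24 then gives a significant result in either direction in 17.6% of trials (nominal 5%), in line with the table.

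The same identity shows how strong each r is, since D = bias/q. With 6 stopping, r = 0.1 means a gap of 0.034/0.2 = 0.17 SD, r = 0.3 means 0.101/0.2 = 0.51 SD, r = 0.5 means 0.169/0.2 = 0.85 SD, and r = 0.7 means 0.237/0.2 = 1.19 SD.

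**4. Interviews**

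Suppose 15 of 30 enrolled patients benefit and k stop. If stoppers benefit as often as the rest, completers show 50%. If a quarter of stoppers benefit, the share is (15 − 0.25k)/(30 − k): 53%, 56% and 61% for k = 3, 6 and 9. If none do, it is 15/(30 − k): 56%, 63% and 71%.

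**5. Partial follow-up**

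If 6 stop and a random 3 of them give 4-week data (n = 27), at r = 0.5 the bias falls from 0.17 to 0.08 SD and the falsely favourable rate from 13.7% to 5.9%. At r = 0.7 they fall from 0.24 to 0.10 SD and from 24.9% to 8.0%.

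**The case against.** The best reply is that this is a small, uncontrolled exploration. Even complete data would not attribute change to VR, and a description of completers with a clear denominator can be legitimate. Patients who had trouble but carried on are still interviewed, and so are completers who saw no benefit. For those who stop under this rule, the broad reason is in the rule itself. The two statements on reassessment can be read as a general rule with an exception. The error rates rest wholly on assumption: the highest need stoppers to change more than 1 SD worse than completers, and the Protocol favours no cell of the table.

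Much of this stands. Bias is not shown, the high-r figures need large gaps, and only some of the accounts of intolerance are lost. Which patients form the main analysis is partly a matter for the analysis plan. Repeating the cognitive test (ECAS) is also a heavier request than a questionnaire.

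The central point is unaffected. The rule governs data collection, so the analysis plan cannot repair it, and the loss of accounts and reasons holds even at r = 0. Being exploratory makes the experience of those who stop more relevant to the aims.

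**Conclusion.** The concern holds and should be fixed before recruitment. As written, the Protocol collects no 4-week scores or interviews from patients who stop because they remain unhappy, does not provide for recording their reasons, and does not fit its own general schedule. That conclusion rests on the text alone, with high confidence.

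The effect on the scores is conditional. It favours VR only if poor tolerance goes with worse change, which is plausible but not shown. Under the assumed 10% to 30% stopping, the bias runs from none (r = 0) to 0.34 SD (30% stopping, r = 0.7). These figures illustrate the range and are not estimates for this trial. The finding does not dispute when VR use should stop.

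**What to change.** Leave the rule for stopping VR as it is and change only what follows from it.

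- Replace the clause that removes the patient with: *The patient stays in the study unless consent is withdrawn, is asked for the reason for stopping, and is offered the interview and the same week-4 questionnaires.*
- Reword the reassessment sentence: *All enrolled patients who remain willing and able will be reassessed and offered the interview, whether or not they are still using VR.* This also reconciles it with the general schedule. State whether the offer includes ECAS.
- Report the number who stopped, with reasons, out of all enrolled. An exact 95% interval shows the precision: 6 of 30 is 20% (8% to 39%).
- In the analysis plan, preferably take all enrolled patients with available data as the main analysis and describe completers separately.

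The cost is a wording amendment plus one set of existing assessments and one short interview for each patient who stops and accepts, so at most 3 to 9 people at 10% to 30% stopping. It asks more of people who stopped while unhappy, so it must remain an offer. Some will decline and some bias will remain. The estimate of benefit may become less favourable.
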